Pharmacogenetics is a promising and novel addition to neuroimaging studies. Twin, family and adoption studies indicate that vulnerability to substance abuse is partially inherited. Individual response to medications will most likely be related to genetic phenotypes. Genetics studies, on their own, require huge sample sizes and are expensive; however, when combined with neuroimaging, which offers a 'picture' of individual brains, we can learn why some individuals respond to a particular medication and others do not. For example, evidence suggests that the rewarding properties of drugs involve activation of the mesocorticolimbic dopaminergic system, and thus, dopaminergic genes will be examined. Candidate dopamine genes include DRD1, DRD2, DRD3, DRD4, DRD5, COMT and DAT. In addition, is also evidence that GABA-ergic mechanisms are involved, particularly the GABA B2 subunit. Therefore, we will examine it as well. The most compelling evidence for a role for variance in dopaminergic components in smoking cue reactivity exists for the dopamine transporter (DAT). Thus, the DAT gene will be our primary focus. The DAT gene has two common polymorphisms. One is the 9 variable number tandem repeat (VNTR) allele and the other is the 10 VNTR allele. Those with the strongest smoking cue responses have at least one 9 VNTR (hetero- or homozygotes) while reduced smoking cue responses occur in those homozygous for the 10 VNTR allele.

OBJECTIVES

1. Overall Objectives

AIM 1 Compare brain and behavioral measures in subjects who are carriers of a dopamine transporter (DAT) 9 (VNTR: 9-repeats) versus 10 VNTR homozygotes (10/10-repeats), actively seeking smoking cessation treatment.

Hypothesis: We will replicate our original findings of differential brain and behavioral responses to cues mediated by variance in the DAT gene. Brain activity will be enhanced in the interconnected ventral striatum and medial orbitofrontal cortex, regions involved in conditioned drug reward, in 9-repeats compared to 10/10-repeats. Brain and behavioral responses will be significantly greater in 9-repeats compared to 10/10-repeats.

AIM 2. Compare brain and behavioral measures following 3 weeks of baclofen versus placebo treatment in treatment seeking subjects.

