Besides smoking cue exposure and withdrawal other factors are involved in smoking behaviors such as continued smoking, craving and relapse. These include attention problems – nicotine enhances attention and some smokers smoke to improve attention (100); menstrual cycle phase – because of the enhanced discomfort of pre-menstrual cycle symptoms and decreased self-efficacy, menstrual cycle phase at start of treatment can affect treatment outcome (6); ability to label feelings – we hypothesize that the inability to label the craving state could be a relapse vulnerability (32); drinking alcohol – drinking alcohol reduces inhibition and often leads to relapse to cigarette smoking (9). Thus, additional measures will be acquired in this protocol that will provide data towards these potential mitigating factors.

CHARACTERISTICS OF THE STUDY POPULATION

1. Target Population:

Patients will be 100 randomized physically healthy and mentally stable male and non-pregnant female patients between the ages of 18 and 60 who smoke 6 or more cigarettes per day for at least 6 months. Subjects will not be excluded based on gender, religion, race, or socioeconomic status. The subject population of previous smoking studies in our lab was 54% female, 62% Caucasian and averaged 15 years of education. This is representative of the urban population in the northeast region of the United States who seek help for nicotine dependence. We expect our current population to have similar characteristics. Thus, women and minorities will be well represented in our study. No special subject groups are included in the protocol.

2. Accrual: 100 randomized (we expect 15 subjects to be lost to attrition)

3. Inclusion Criteria:

- 1) Physically healthy, as determined by a comprehensive physical examination and approval of the study physician males or females who smoke cigarettes, ages 18-60.
- 2) Smoke \geq 6 cigarettes per day for at least 6 months prior to study start date.
- 3) Females must be non-pregnant, non-lactating and either be of non-childbearing potential (i.e. sterilized via hysterectomy or bilateral tubal ligation or at least 1 year post-menopausal) or of child bearing potential but practicing a medically acceptable method of birth control. Examples of medically acceptable methods for this protocol include barrier (diaphragm or condom) with spermicide, an intrauterine device (IUD), the Nuvaring, oral contraceptives, levonorgestrel implant, hormonal injection or complete abstinence.

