Non-abstinent subjects will be randomized by sex and DAT genotype. We will use our perfusion fMRI/cue paradigm to acquire resting baseline (RB) and SC data to confirm and extend our finding of a DAT-mediated SC-vulnerable endophenotype; 9-repeat carriers will exhibit enhanced brain activity in the interconnected VS/mOFC (regions involved in conditioned drug reward) compared to 10/10-repeats. Behavioral responses, including craving and cigarette consumption, will be significantly greater in 9-repeat carriers compared to 10/10-repeats following SC exposure.

Within the 2 x 2 design (9-repeat carriers vs 10/10-repeats) X (baclofen vs placebo), treatment-seeking subjects will participate in an 8-week medication regimen. Baclofen or placebo will be prescribed to non-abstinent subjects at the same doses that have been demonstrated to be clinically effective in our Smoking Reduction Trial. The importance of subjects being non-abstinent is twofold. First, our goal is to determine if and how baclofen affects SC reactivity independent of WD to disentangle these two major motivators underlying relapse. Second, differences in smoking behavior modulate brain activity, so it is important that baclofen- and placebo-treated groups have similar smoking characteristics.

3. Study Duration

This study requires a one-week screening phase and 8 weeks of monitoring and medication. All subjects will complete 2 MRI sessions (one before starting medication, one following 3 weeks of medication) and 5 weeks of additional treatment. Each subject will be enrolled in the study for approximately 10 weeks.

The entire study will commence 12/01/2012 and will run until 08/31/2017, approximately. 20 to 25 subjects will be randomized each year.

DRUGS OR DEVICES

Baclofen and matching placebo

STUDY PROCEDURES

General Procedures

*Interested potential subjects will be screened with a structured interview. Individuals who may qualify are scheduled for the consenting visit. If the consent is successful, individuals will be scheduled to come in for physical and psychological examinations and to provide a genetics sample.

*After the results of the examinations are reviewed, the subject will be contacted to inform them whether or not they qualify. If the examinations reveal any health problems that require medical attention, the subject will be referred to their family physician.

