*Part of the physical ** Part of the Psych Eval *** Collected pre- and post scan ⁺ Occurs the same day as the Quit Wk appt

2. Analyses

Imaging Data Processing: Prior to performing analyses, brain data are examined for gross movement and full image acquisition. An SPM-based ASL data processing toolbox is used for data analyses. ASL image pairs are realigned to the mean of all control images and spatially smoothed with a 3D isotropic Gaussian kernel with FWHM of 10mm. CBF image series are generated using a simplified two-compartment model with the sinc interpolation method for CBF calculations. The mean control image of each subject's data is co-registered to a HR 3D T1 structural image using the mutual information based co-registration algorithm provided by SPM8. The same co-registration parameters are used to co-register the CBF maps to the structural image. The structural image is then spatially normalized to the MNI standard brain. The same parameters are used to normalize the CBF images to the MNI standard space. Each subject's normalized mean control images are segmented using SPM8. The segmented gray matter masks are averaged and the overlap of subject's gray matter is extracted. This final mask is used for calculating global CBF for each session.

Imaging Data Analyses: Voxel-wise analyses of the CBF data are conducted on each subject using a general linear model (GLM). Global CBF time course is included in the model as a covariate to examine the effects of baclofen. Analyses are conducted on absolute (RB) and relative (during SC exposure) CBF. No temporal smoothing is applied. Contrasts between conditions (Time 1 versus Time 2) are defined in the GLM model to assess the voxel by voxel CBF difference. Using the corresponding parametric maps of this contrast (maps), random effects analysis is employed to test for a significant main effect of condition with a SPM map of the T statistic at each voxel for population inference for each session for the placebo and baclofen groups (second-level analysis). A 2x2 factorial design matrix is used to assess the effects of the pharmacological manipulation by including the group (baclofen vs placebo) and condition (Time 1 vs Time 2) as the two factors. This two-stage analysis is theoretically equivalent to a 2 way ANOVA.

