We have recently gained expertise in connectivity analysis, which we will utilize here as in our previous studies. This approach determines the degree to which the time course of each voxel correlates with the averaged time course from a specific region of interest (e.g., the VS/mOFC). In this approach, the time course of all voxels within this region of interest will be extracted, and the averaged time course will be used as the regressor to check the correlation between the seed region and the rest of brain. As an alternative, we can repeat the same correlation analysis but using the principal component of all time courses extracted from the ROI as the reference function. For each subject, the β map of the voxel wise connectivity analysis (correlation analysis) will be collected, and group analysis through random effects using one-sample t-tests will be performed to assess the across-subject effects of the brain connectivity to the seed region of interest. Neuropsychological and behavioral scores can be used as simple regressors to examine their relationship to connectivity for a brain target. Though our focus for the project is VS/mOFC connectivity due to its role in emotional arousal, the same analyses can be performed for other regions of interest (e.g., lateral OFC).

Behavioral Analyses: Statistical significance tests use an alpha of .05 unless otherwise noted. Continuous demographic variables (e.g., age, education, FTND, CPD, pack years, TAS, RSQ, SJ, mCEQ and the CWQ composite scores, latency to smoke, and cigarette consumption) are checked for normality, transformed if necessary, and summarized by calculating means, standard deviations and ranges. Scores on each factor will be included as covariates of interest with respect to perfusion fMRI SC data and genetic variance in DA-ergic components. Analysis of variance will be used to assess demographic differences across groups. Nominal demographic variables (e.g., race, sex, genotype) are summarized by calculating proportions and compared across groups using chi square analyses. Demographic (age, years education, monthly income) and clinical (depression, anxiety and psychiatric symptom scores) will also be summarized and compared across the treatment groups.

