Changes to the CRF and the study database are strictly monitored. After a single line is drawn through the corrected data point, the RT documents the change by placing his or her initials and the date of the change adjacent to the correction. Typical QA responsibilities of the RT include:

- Checking all data during or immediately after study visits.
- Checking charts at predetermined points during the study (initials and date of checker are required on each form checked).
- Performing the initial data check after a few charts have been entered.
- Performing a 10% data check when all data have been entered.

Typical responsibilities of the PI include:

- Monitoring and reporting on RT interviewing and data collection proficiency at subject study visits.
- Checking charts at predetermined points during the study (initials and date of PI are required on each form checked).
- Supervising study database checks.
- When databases, in Filemaker Pro or other applications, are developed by the research staff, only the data checked by the RT are entered. Data sets are double checked in pairs by technicians. The PI supervises any corrections to the data set and reviews the completed database before the information is used in any reports or analyses.
- The PI holds meetings with the RTs to report and review the project and data entry status.
- PI reviews lab results and screening information (inclusion/exclusion checklist) for potential subjects.
- PI reviews adverse events on at least a weekly basis

Study Logs and Reports

Study logs are routinely maintained in order to keep computerized back up records of subjects identifying and socio-demographic characteristics and experimental group status. The study subject log usually includes subjects' initials, study number, CRF number, date of birth, race, medication start dates, subject status (active, drop-out, completer, follow-up) and relevant dates and comments.

Data Storage on Site

The CRFs and research charts are stored in file rooms specifically designed for data storage. All study data are housed in locked file cabinets. Only designated members of the research team have access to the file cabinets containing research data. Data are kept on site for not less than three years after the subject has completed the final assessment. Data are then eligible for archiving.

9. APPENDIX 1: (Sub-study) Baclofen effects on brain and behavior in treatment-seeking cigarette smokers who drink heavily

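### Aim 1 compares genotype groups that are not randomised, and race, which is recorded, is not among the covariates named for that comparison

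*Combined protocol and SAP*

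**What the plan says.** - **The contrast.** Objectives, Aim 1: "Compare brain and behavioral measures in subjects who are carriers of a dopamine transporter (DAT) 9 (VNTR: 9-repeats) versus 10 VNTR homozygotes". The Primary Outcome section opens with the same genotype comparison.
- **What is randomised.** Study Design, section 2: "Non-abstinent subjects will be randomized by sex and DAT genotype". Treatment is assigned within sex and genotype. Race is not a stratum.
- **The expected sample.** Target Population gives the lab's earlier samples as "54% female, 62% Caucasian and averaged 15 years of education" and adds: "We expect our current population to have similar characteristics".
- **Race is recorded.** Study Logs and Reports lists "subjects' initials, study number, CRF number, date of birth, race" among the items in the subject log.
- **What is done with race.** Behavioral Analyses: "Nominal demographic variables (e.g., race, sex, genotype) are summarized by calculating proportions and compared across groups using chi square analyses". The sentence does not say whether the groups are genotype or treatment groups, and it attaches no consequence to the result.
- **Covariates that are named.** Imaging Data Analyses: "Global CBF time course is included in the model as a covariate to examine the effects of baclofen". Behavioral Analyses: "Scores on each factor will be included as covariates of interest with respect to perfusion fMRI SC data and genetic variance in DA-ergic components", which follows a list of continuous variables such as age, education, FTND and cigarettes per day. Race is nominal and appears only in the later chi-square sentence.
- **Genetic checks.** Genetics Analysis plans Hardy-Weinberg testing and duplicate genotyping as quality control. No ancestry markers or race-stratified analysis are mentioned.

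**The concern.** A comparison of inherited genotypes is observational. If 9-repeat carriers and 10/10 homozygotes differ in racial make-up, and cue response or smoking behaviour also differs by race, part of the genotype contrast reflects race and not DAT. The plan collects the variable that would deal with the measured part of this but does not put it in the model. At stake is the interpretation of the gene, brain and behaviour link that Aim 1 is meant to establish. The background already reports this contrast from two cohorts, so the new estimate should be as free of avoidable bias as the collected data allow.

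**Working it through.** **Inputs from the documents.** Share Caucasian w = 0.62. 100 randomised, 15 expected lost, so 85 remain. The first scan precedes randomisation (General Procedures), so about 100 is the relevant number for Aim 1; both are shown. Alpha is 0.05, taken as two-sided because the plan does not say. Planned genotype effects are d = 0.78 (VS) and 0.98 (OFC).

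**Inputs assumed, because the documents give none.** 9-repeat carrier share in Caucasian subjects (a) v others (b): 50% v 40% to 55% v 25%, with equal shares as the null case. Outcome difference by race, δ: 0.3 to 0.8 SD (SD within genotype group). The remaining 38% are treated as one group.

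**Step 1. The plan's own figure.** n per group = 2(1.96 + 0.842)²/d² = 15.70/d².
- d = 0.98: 16.3, so 17 (18 by exact t).
- d = 0.78: 25.8, so 26 (27 by exact t).

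The stated range is 18 to 24, so the upper end is slightly optimistic. These effects serve here only as the scale for the bias.

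**Step 2. Imbalance in race between genotype groups.** Overall carrier share p = wa + (1 − w)b. Share Caucasian among carriers = wa/p; among 10/10 homozygotes = w(1 − a)/(1 − p).
- 50% v 40%: p = 0.310 + 0.152 = 0.462. Shares 0.310/0.462 = 0.671 and 0.310/0.538 = 0.576. Difference 0.095.
- 55% v 25%: p = 0.341 + 0.095 = 0.436. Shares 0.341/0.436 = 0.782 and 0.279/0.564 = 0.495. Difference 0.287.
- Equal shares: difference 0.

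**Step 3. Bias and false-positive rate, true DAT effect zero.** Bias = difference × δ. The rejection rate comes from the noncentral t with noncentrality bias/√(1/n₁ + 1/n₂), where n₁ = Np and n₂ = N(1 − p).

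| Carrier shares | δ | Bias (SD) | Rejects, n=85 | Rejects, n=100 |
|---|---|---|---|---|
| equal | any | 0 | 5% | 5% |
| 50% v 40% | 0.3 | 0.095 × 0.3 = 0.03 | 5% | 5% |
| 50% v 40% | 0.8 | 0.095 × 0.8 = 0.08 | 6% | 7% |
| 55% v 25% | 0.3 | 0.287 × 0.3 = 0.09 | 7% | 7% |
| 55% v 25% | 0.5 | 0.287 × 0.5 = 0.14 | 10% | 11% |
| 55% v 25% | 0.8 | 0.287 × 0.8 = 0.23 | 18% | 20% |

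Worst case at n=85: √(1/37.06 + 1/47.94) = 0.219, noncentrality 0.230/0.219 = 1.05. Against the planned effects, 0.23/0.78 = 29% and 0.23/0.98 = 23%.

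**Step 4. Would the planned checks reveal it?** Race-by-genotype chi-square at n=85 (52.7 v 32.3 subjects):
- 50% v 40%: SE = √(0.25/52.7 + 0.24/32.3) = 0.110, z = 0.91, power Φ(0.91 − 1.96) = 0.15.
- 55% v 25%: SE = 0.102, z = 2.93, power Φ(0.97) = 0.83.

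Hardy-Weinberg test, noncentrality N·F². Assuming equilibrium within each race group, 55% v 25% gives 9-allele frequencies of 0.329 and 0.134, and F = 0.2356 × 0.195²/(0.255 × 0.745) = 0.047. At N=100 the noncentrality is 0.22 and power about 0.08.

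**Step 5. Cost of adjusting.** Variance inflation = 1/(1 − φ²), with φ² = difference² × p(1 − p)/[w(1 − w)].
- 50% v 40%: φ² = 0.009, inflation 1.01.
- 55% v 25%: φ² = 0.086, inflation 1.09.

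In the second case at n=85, noncentrality for d = 0.78 is 0.78/√(0.0478 × 1.094) = 3.41, so power remains about 0.92.

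**Step 6. Aim 3.** Within genotype g, the baclofen-minus-placebo difference is τ + γ × (share Caucasian in g), where γ is any race-by-treatment effect. A race main effect δ cancels, because race is balanced between arms in expectation within each genotype. The interaction is therefore biased by γ × difference: zero when γ = 0, and 0.8 × 0.287 = 0.23 SD when γ = 0.8 in the worst case. Simulation at n=85 with 2:1 allocation agrees. With δ = 0.8 and γ = 0 the bias is 0.00. With γ = 0.8 it is about 0.23 both without and with a race main effect in the model, and about zero once race-by-treatment is added.

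**The case against.** The strongest reply is that the harm needs two differences, in allele frequency and in outcome by race, and the documents report neither. That stands: the ranges are assumptions, the true bias may be zero, and the top figures need both extremes at once, including a race effect (0.8 SD) as large as the planned VS effect.

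A second reply is that the cue contrast is within person (smoking v non-smoking cues), so a race difference in overall blood flow largely cancels. That also stands for the cue contrast, where only a difference in reactivity matters. It does not cover resting flow, which is analysed in absolute terms, or the behavioural measures.

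Third, the plan does name covariates, does compare race across groups and does test Hardy-Weinberg equilibrium. These are fair context, but none puts race in the genotype model, and Step 4 shows that the two checks can miss the imbalance. Nor does the plan say that the chi-square decides whether to adjust, so it should not be criticised for that.

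A reader might go further and infer that the genotype-by-treatment interaction in Aim 3 is equally exposed. The documents do not support this. Treatment is randomised within genotype, so a race main effect drops out (Step 6). Only modification of the baclofen effect by race would matter, and nothing in the documents indicates it. A reader might also want sex added on the same grounds, but no confounding path through sex is shown.

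**Conclusion.** The point holds for Aim 1 as a cheap improvement in protection from bias. The contrast is observational, a racially mixed sample is expected, and a recorded variable is left out of the named covariates. The possible bias is 0 if either difference by race is absent, and 0.03 to 0.23 SD over the assumed ranges, with rejection under no DAT effect of about 5 to 18% (n=85) or 5 to 20% (n=100).

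A reader might infer that a positive Aim 1 result would be an artefact of race. The figures do not support that: even the extreme case reaches less than a third of the smaller planned effect. The documents also do not show that confounding by race exists, only that the plan does not guard against it. Aim 2, a randomised comparison, is unaffected. The Aim 3 interaction is not biased by a race main effect.

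**What to change.** In Imaging Data Analyses and Behavioral Analyses, state that race enters as a covariate in every Aim 1 genotype model, imaging and behavioural, whatever the chi-square shows. Say whether the groups in the chi-square sentence are genotype or treatment groups. Pre-specify a sensitivity analysis that repeats the Aim 1 contrast within the largest race group. At 62% of 100 that is about 62 subjects, or 31 per genotype group at a 50% carrier share, which still exceeds the planned 18 to 24.

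For Aim 3, a race main effect alone would not help. If effect modification by race is a worry, add one sensitivity analysis with race and race-by-treatment.

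The cost is wording, one or two degrees of freedom, and variance inflation of about 1.0 to 1.1. No new data are needed. Race is only a proxy for ancestry, so some confounding could remain, and the report should say so.

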Wechsler Abbreviated Scale of Intelligence (WASI) is a brief and reliable measure of intelligence that provides an estimate of an individual's IQ scores. We will use the two subtest form (vocabulary and matrix reasoning) that offers an estimate of an individual's cognitive functioning. Individuals with an intelligence quotient of ≤ 80 are excluded because they do not have the cognitive skills necessary to participate in several of the study components. (administration time: approximately 15 mins).

Following these procedures, [name] will meet with the assessing clinician to discuss any subject reservations. For subjects who we feel may need additional eligibility verification, we would like to have the option to view their medical records. In these instances, we will first check EPIC to see if the subject has an EMR. If they do not, we will work with the subject and their PCP to obtain the appropriate medical releases to obtain information on their recent medication use and diagnoses, when available.

Prospective subjects will be notified of their eligibility by telephone within 5 business days after the physical and psychological evaluations. This waiting period is necessary to examine results from laboratory and psychological tests to determine whether the subject meets eligibility requirements (i.e., if all values and scores fall within normal limits).

1st MRI session Visit (approximately 3 hours)

Stimuli used will be audio-visual video clips consisting of either smoking-related cues: individuals differing in race, age and sex who are smoking and using explicit language designed to induce appetitive desire for a cigarette; or non-smoking-related cues that are similar in content, but individuals relate interesting short stories that do not portray cigarette smoking or smoking reminders. Two similarly-valenced cue sets will be employed (counterbalanced) to control for habituation that may occur at Time 2. In prior studies, our SCs elicited robust reward-related neuroactivity and subjective craving responses, in conjunction with strong brain/behavioral correlates.

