The Alcohol Urge Questionnaire (AUQ) (Bohn et al., 1995) is an 8-item, self-administered state measure assessing the urge for an alcoholic drink at the time the questionnaire is completed and provides an index of acute craving. The AUQ contains four items pertaining to the desire for a drink: two items regarding expectations of positive effects from drinking, and two items relating to the inability to avoid drinking if alcohol were present. This measure has strong correlations with measures of alcohol dependence and severity.

Timeline Follow Back (TLFB): The TLFB will be used to measure subjects' alcohol use. Baseline 30-day TLFB is administered at the pre-treatment scan (week 1). At the on-treatment scan TLFB is acquired to measure use between baseline and present. Finally, at the follow-up visit the TLFB will cover the last month.

Randomization: Subjects will be unequally randomized at a rate of 2 baclofen to 1 placebo. Study medication, supplied by Watson Pharmaceuticals, will be packaged in blister packs for individual subjects and supplied by the HUP Investigational Drug Service to the study medical staff who will monitor and dispense the medication. The randomization schedule will be available in the hospital pharmacy 24 hours a day in the event of an emergency. Baclofen will be prescribed at 20 mg 4 times per day. Each baclofen pill will be 10 mg. Thus, 2 pills will be taken at each scheduled dose for a total of 8 pills a day. In this way, the titration schedule, taper and potential dose reductions can be managed. Placebo-treated subjects will follow the identical schedule. This dose was chosen based on the results from our *Baclofen for Smoking Reduction Study* wherein we found this dose to be effective at reducing the number of cigarettes smoked per day(72).

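### Cue set is counterbalanced across the two scans but left out of the cue-exposure CBF model, so any difference between the sets stays in the error of the Time 1 v Time 2 contrast

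*Combined protocol and SAP*

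**What the plan says.** The stimuli paragraph under 1st MRI session Visit reads: "Two similarly-valenced cue sets will be employed (counterbalanced) to control for habituation that may occur at Time 2". The natural reading is that each subject sees one set at Scan 1 and the other at Scan 2, with the order varied between subjects. The unit of balance (overall, or within arm, genotype or sex) is not given.

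Under 2. Analyses, Imaging Data Analyses:
- Subject-level contrast: "Contrasts between conditions (Time 1 versus Time 2) are defined in the GLM model to assess the voxel by voxel CBF difference".
- Covariate: "Global CBF time course is included in the model as a covariate to examine the effects of baclofen".
- Second-level 2x2 model, built "by including the group (baclofen vs placebo) and condition (Time 1 vs Time 2) as the two factors". The same section also tests the time effect separately in the placebo and baclofen groups.
- Measures: "Analyses are conducted on absolute (RB) and relative (during SC exposure) CBF".

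Behavioral Analyses adds: "Scores on each factor will be included as covariates of interest with respect to perfusion fMRI SC data and genetic variance in DA-ergic components". The variables listed there are demographic, smoking and questionnaire measures. Cue set and order are not among them.

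On allocation, Study Design says: "Non-abstinent subjects will be randomized by sex and DAT genotype". The Randomization paragraph says: "Subjects will be unequally randomized at a rate of 2 baclofen to 1 placebo". Cue-set order is not a stratum, and General Procedures lists the first scan before randomisation.

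**The concern.** Counterbalancing makes cue-set order a design factor. It prevents set from being confounded with time on average, but it does not remove the set difference from an individual's data. A subject shown set A and then set B carries the difference with one sign in the Time 2 minus Time 1 map, and a subject shown B and then A carries it with the other. A model with only arm and time treats this known, systematic component as random error.

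The plan describes the sets as alike in valence. Nothing says that they evoke equal cerebral blood flow, or that order is balanced within arm or genotype. At stake are some precision in the drug contrast for cue reactivity and, in any one realised sample, a shift in an estimate if order happens to be uneven. The within-arm tests have no second arm against which the set effect can cancel. For the Aim 1 genotype contrast the route is different: what matters is which set was shown at Scan 1. Randomisation to arm does nothing to balance that across genotypes.

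**Working it through.** **The plan's own figure.** The sample-size paragraph gives 18 to 24 per group for effect sizes of 0.98 (OFC) and 0.78 (VS). The two-sided normal formula at alpha 0.05 and 80% power gives 17 and 26, each within two subjects of the stated ends. At 24 per group and 0.78, two-sided power is 0.77 (normal) or 0.75 (t-test). These figures concern genotype. The plan gives no power figure for the Time 1 v Time 2 drug contrast and makes no allowance for cue set.

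**Inputs from the plan.** There are 100 randomised and 15 expected losses, leaving 85. At 2:1 that is about 57 v 28. Alpha is 0.05, taken here as two-sided.

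**Assumption.** The set difference s is not in the documents. It is taken as 0.1 to 0.5, in SDs of the within-order change score.

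**Model.** Change score D = arm effect + o x s + error, with o = +1 or -1 for order and error SD 1.

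**Step 1: precision.** With order split evenly, Var(D) = 1 + s². The standard error of the arm contrast without a set effect is sqrt(1/57 + 1/28) = 0.231. The effect with 80% power is (1.960 + 0.842) x 0.231 = 0.647 SD. With order ignored, power = Φ(2.802/sqrt(1 + s²) - 1.960).

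| s | Variance increase | Power |
|---|---|---|
| 0.1 | 1% | 79.6% |
| 0.2 | 4% | 78.4% |
| 0.3 | 9% | 76.5% |
| 0.5 | 25% | 70.7% |

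**Step 2: shift given an imbalance.** The arm contrast moves by 2 x s x (difference between arms in the share with one order). At a 20-point difference this is 0.04, 0.08, 0.12 and 0.20 SD for the four values of s. If order is balanced only overall, the chance of a difference of at least 20 points is 11% at 57 v 28. Within one genotype stratum (assumed 28 v 14) it is 33%. Conditional on a 20-point difference at 57 v 28, simulated type I error without adjustment is 0.061, 0.069 and 0.096 for s = 0.2, 0.3 and 0.5. With order in the model it is 0.050.

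**Step 3: steps 1 and 2 are one effect.** Under random order the shift has mean zero and SD s x 0.231. Its variance, s² x 0.231², is exactly what step 1 adds to the squared standard error: 0.231² x (1 + s²). Averaged over orders, the unadjusted test keeps its level. Simulated type I error was 0.049 even with a set difference of 0.5 single-session SD and a between-scan correlation of 0.7.

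**Step 4: within-arm tests.** The mean change in one arm shifts by s x (2p - 1), where p is the share with one order. With 22 in an arm, the size reported in the results summary at the end of the document, a 14:8 split gives s x 6/22 = 0.27s.

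**Step 5: Aim 1 at Scan 1.** Here s is in between-subject SDs of the Scan 1 response. The added variance is 0.25s², or 0.25% to 6.25%. A 20-point imbalance between genotype groups in the set shown moves the contrast by 0.2s, or 0.02 to 0.10 SD.

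**Step 6: which term removes it.** In a group x time model the set effect has opposite signs at the two scans, so it is an order-by-time effect. A between-subject main effect of order adjusts only each subject's mean over the two scans, and leaves the group x time estimate unchanged. The set shown at each scan, equivalently order x time, does remove the effect, as does order as a covariate on the change map.

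**The case against.** The strongest reply is that counterbalancing already does the main job. Set is not confounded with time on average, and randomisation makes the arm shift zero in expectation. This stands. A reader might infer that the omission biases Aims 1 to 3. The documents do not support that for the randomised comparison, where the chance shift is the same quantity as the lost precision (step 3). Nor does it apply to every outcome: resting CBF, cotinine and cigarettes per day carry no cue-set effect. For genotype, arm randomisation gives no protection, but a shift still requires an actual imbalance in the set shown, and none is documented.

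The size is also open. The sets are matched for valence, and the non-smoking clips are described as similar in content to the smoking ones. If matched clips belong to the same set and the smoking minus non-smoking response is analysed, features common to both cancel, and only a set difference in that contrast remains. A reader might infer a much larger loss. A set difference of 0.5 single-session SD with a between-scan correlation of 0.7 gives 0.5²/[2(1 - 0.7)] = 42% more variance and power of 65%. That is the corner of two assumed ranges, since the documents give neither quantity, and 0.5 SD would be about two-thirds of the plan's own VS genotype effect (0.5/0.78 = 0.64).

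Finally, it could be said that the genotype part adds a covariate to a model the plan has not written, because the 2x2 has no genotype factor. That is true. The covariate belongs in whatever genotype model is specified.

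None of this answers the core point: a factor built into the design is missing from the analysis.

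**Conclusion.** The point holds for cue-exposure outcomes: CBF during cues, and craving if it is analysed the same way. Cue set is a known design factor that the written model leaves in the error term. Under the assumed 0.1 to 0.5 SD of the change score, variance rises by 1% to 25% and 80% power becomes 79.6% to 70.7%. At 0.1 to 0.2 SD the loss is 0.4 to 1.6 percentage points of power; it becomes material from about 0.3 SD, or in small subgroups where order can easily be uneven. Shifts in the arm, within-arm or genotype estimate depend on the realised imbalance, which the documents do not report. This is an inexpensive improvement to a stated model. It is not evidence that the drug comparison is biased or that the counterbalancing has failed. The figures rest on the assumed set difference, 57 v 28 completers, two-sided alpha 0.05, and the reading that each subject sees a different set at each scan.

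**What to change.** Amend Imaging Data Analyses, before the data are analysed, so that:
- the set shown at each scan is recorded for every subject, and the unit of counterbalancing is stated;
- in the group x time model for cue-exposure CBF, cue set enters as a within-subject factor (equivalently order x time). Order as a between-subject main effect alone is not enough (step 6);
- where Time 2 minus Time 1 maps are analysed, including the within-arm tests, order enters as a covariate, coded +1/-1 so that the mean change refers to an even split;
- in the Aim 1 genotype contrast, the set shown at Scan 1 enters as a covariate.

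The same terms should go into the craving analysis if it compares the two scans. The cost is one degree of freedom and a record of the set shown. A reader might assume that this record already exists because the sets are counterbalanced, but the Table of Measures does not list it, so it should be confirmed.
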